#### **14.5 Safety Analysis**

For the safety analysis, descriptive statistics such as mean, median, minimum, maximum, and standard deviation will be summarized for continuous variables. Frequency distributions will be summarized for categorical variables. Since all subjects will receive vehicle on the dominant arm in addition to blinded study drug on the non-dominant arm, some subjects will receive both active and vehicle treatments. All safety-related data will be summarized as an overall group except AEs related to the area of application.

Adverse events will be coded using the Medical Dictionary for Regulatory Activities (MedDRA) version 19.1 (or higher). For summary tables, AEs coded to the same preferred term will be counted only once within a given subject. If an AE was recorded on multiple occasions in the same treatment period, only the highest severity and the highest degree of relationship to the study drug will be presented. If 2 or more clinical events are reported within a single AE entry, then the corresponding individual preferred terms will be coded separately.

All AEs, including those that are not treatment-emergent, will be listed. All summaries of AEs will be of TEAEs. A TEAE is defined as an AE that is new or worsened in severity after the first dose of study drug. Adverse events will be summarized by system organ class (SOC), and preferred term. Summaries will be prepared for all AEs, treatment-related AEs, and SAEs. The AE summary will also be presented with a breakdown by severity. Adverse events that are specific to the arm, such as application site reactions, will be summarized by treatment (active versus vehicle).

Changes from baseline in chemistry, hematology, coagulation, and urinalysis parameters will be summarized descriptively. Laboratory results will be classified as low, normal, or high according to the laboratory-supplied reference ranges. Shift tables describing out-of-range shifts from

baseline (in frequency counts) will be created and presented by treatment. All laboratory results will be listed.

The results of physical examinations will be summarized by body categories with frequency and percentages of normal versus abnormal, and if abnormal whether it is clinically significant or non-clinically significant. A listing of physical examination results will be presented by subject and assessment time point.

Results of the ECGs will be presented as normal, abnormal (clinically significant), and abnormal (not clinically significant). These results will be listed by subject and summarized descriptively.

Vital signs will be listed by subject and summarized descriptively by time point.

Prior and concomitant medications will be coded using the World Health Organization (WHO) Drug Dictionary and summarized descriptively. Prior medications are defined as any medications started prior to the day of the first dose of study drug. Concomitant medications are defined as any medications taken on the day of or after the first dose of study drug. Prior and concomitant medications will be coded using the WHO Drug Dictionary version of September 2014. A by-subject listing will be generated that contains both prior and concomitant treatments. Medications will be classified according to primary 4th level Anatomical Therapeutic Chemical codes and WHO Drug preferred terms in the listing. Subjects may have more than 1 concomitant treatment per drug class and per preferred term. Summary tables will be generated by treatment for both prior and concomitant treatments. In these summary tables, a subject will be counted only once for a given prior or concomitant treatment. Prior and concomitant non-medicinal therapies (non-drug treatments) will be coded using MedDRA and then summarized in a similar manner as prior and concomitant medications.

CBI

CBI

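### Section 14.5 pools systemic safety data across the randomised groups and contradicts its own by-treatment laboratory shift tables

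*Combined protocol and SAP*

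**What the plan says.** Section 14.5 first describes the two-arm application: "all subjects will receive vehicle on the dominant arm in addition to blinded study drug on the non-dominant arm", with the consequence that "some subjects will receive both active and vehicle treatments". The next sentence gives the reporting rule: "All safety-related data will be summarized as an overall group except AEs related to the area of application". That exception is the only one stated.

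The section then lists its outputs. For adverse events, "Summaries will be prepared for all AEs, treatment-related AEs, and SAEs", with a further breakdown by severity; arm-specific events are shown active versus vehicle. For laboratory data, "Changes from baseline in chemistry, hematology, coagulation, and urinalysis parameters will be summarized descriptively", and tables of out-of-range shifts "will be created and presented by treatment". Physical examinations and ECGs are summarised with no grouping named. For vital signs, "Vital signs will be listed by subject and summarized descriptively by time point". For medications, "Summary tables will be generated by treatment for both prior and concomitant treatments".

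Elsewhere, section 8 describes a vehicle-controlled, parallel-group trial meant to determine both efficacy and safety. Section 7.1 makes safety of the active product the secondary objective. Sections 14.2 and 14.3 give 1:1 allocation and 250 subjects, 125 per group. Section 14 leaves detailed methods to a separate SAP.

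**The concern.** There are two problems.

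- **The text conflicts with itself.** Laboratory shift tables are safety data and are not adverse events at the application site. The overall-group rule therefore covers them, while their own sentence requires them by treatment. Whoever programs the tables must choose which instruction to break.
- **The rule discards the control group where it is needed.** For systemic safety, a vehicle group lets a reader separate effects of AP0302 from the background of exercise, inpatient stay and vehicle. If the main tables show one merged column, an excess on AP0302 looks the same as a background rate shared by both groups.

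The position of the rule, directly after the description of dominant-arm vehicle, suggests that the mixed exposure is why the groups are merged. The plan does not say so; the link is inferred from the order of the sentences. If it is the reason, it does not support the rule.

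**Working it through.** **Step 1. Set the outputs of section 14.5 against the rule.**

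| Output | Grouping in its own sentence | Under the overall-group rule |
|---|---|---|
| TEAEs, treatment-related AEs, SAEs, severity (not arm-specific) | none | pooled |
| Arm-specific AEs | by treatment | covered by the exception |
| Laboratory change from baseline | none | pooled |
| Laboratory shift tables | by treatment | **conflict** |
| Physical examination, ECG, vital signs | none | pooled |
| Prior and concomitant medications | by treatment | arguably not safety outcomes, so a weaker mismatch |

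Where an output names no grouping, the general rule is the only instruction in the document.

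**Step 2. Does dominant-arm vehicle prevent a comparison?** Each subject is randomised to one product for the non-dominant arm (sections 8 and 14.5), and all subjects get vehicle on the other arm. The groups are:

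- AP0302 group: AP0302 + vehicle
- Vehicle group: vehicle + vehicle

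The dominant-arm vehicle is the same in both, so it cannot confound the randomised contrast. It matters only for deciding which arm a local event belongs to, and arm-specific events are already reported by treatment.

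**Step 3. Does the treatment-related table restore the contrast?** No. Section 12.4 judges relatedness to the investigational product, and under section 9.4 site staff do not know whether a tube is active or vehicle. Blinded assessment is proper, but the resulting table combines events attributed to either product.

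**Step 4. What a pooled rate can show.** Inputs: 250 subjects at 1:1, so 250 × 1/2 = 125 per group, which agrees with section 14.3. Let v be the vehicle rate, a the AP0302 rate, and d = a − v.

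Pooled rate = (125v + 125a)/250 = (v + a)/2 = v + d/2

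The pooled rate lies d/2 above the vehicle rate and d/2 below the AP0302 rate. For example, 3 events all on AP0302 are 3/125 = 2.4% of that group but 3/250 = 1.2% pooled. Since v is not shown, d cannot be recovered.

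For a pooled count k (no more than 125), with x events on AP0302, the difference is (x − (k − x))/125 = (2x − k)/125. As x runs from 0 to k, this runs from −k/125 to +k/125. The counts below are assumed, because the documents give no event rates.

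| k | Pooled rate k/250 | Possible difference, percentage points |
|---|---|---|
| 3 | 1.2% | −2.4 to +2.4 |
| 6 | 2.4% | −4.8 to +4.8 |
| 12 | 4.8% | −9.6 to +9.6 |

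For k = 6, a split of 6 v 0 is 4.8% v 0%, 3 v 3 is 2.4% in each group, and 0 v 6 is 0% v 4.8%. All three print as 2.4%.

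For k = 12, a split of 10 v 2 is 8.0% v 1.6%, a difference of 6.4 points (Fisher exact p = 0.034). The pooled table would print 4.8%. The p-value only shows how marked a contrast could go unseen; the plan tests no safety outcome, and none is asked for.

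**The case against.** The strongest reply is that the general sentence was never meant to govern everything. The section itself presents shift tables and medications by treatment, so the specific sentences could be read as overriding the general one, and the outputs that name no grouping could be settled in the separate SAP. Nothing is lost irretrievably, because laboratory results, ECGs, vital signs and adverse events are also listed. Safety is descriptive, no decision rule depends on it, and efficacy is untouched. The plan also never states that dominant-arm vehicle is its reason for pooling.

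Part of this stands. The final table layout cannot be known from the protocol, and the inference about the rationale is only an inference. The by-treatment shift tables and arm-specific AE tables do keep some of the comparison. The text of the local tolerability subsection (14.5.1) is not visible, so nothing is inferred from it. The event counts above are illustrative and measure nothing observed in this trial.

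The rest does not rescue the sentence. An override reading would settle the shift tables but would leave adverse events, laboratory change, vital signs, ECGs and physical examinations under the general rule. A SAP that follows the protocol inherits both the rule and the contradiction, and an unseen SAP cannot be assumed to reverse it. Subject listings would have to be re-tabulated by treatment, and the visible text does not say that they show treatment. A descriptive table also needs its comparator column to be interpreted.

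**Conclusion.** The concern holds, with high confidence on the text. The overall-group rule and the by-treatment shift tables cannot both be followed, and nothing else in the document reconciles them. Applied literally, the rule merges about 125 AP0302 and about 125 vehicle subjects in the main systemic safety tables of a vehicle-controlled trial whose secondary objective is AP0302 safety. The merged rate carries no information on the group difference: for k pooled events the difference can lie anywhere within ±k/125, for example ±4.8 points when k = 6.

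This assumes that the Safety Population is close to the planned 125 per group and that outputs with no stated grouping follow the general rule. The point should be fixed. It concerns reporting only; data collection, efficacy analysis and sample size are unaffected.

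**What to change.** Replace the overall-group sentence in section 14.5 with wording such as:

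> Summaries of TEAEs (overall, by SOC and preferred term, by severity, treatment-related, and serious), laboratory results, vital signs, ECGs and physical examinations will be presented descriptively by treatment group, defined by the product received on the non-dominant arm (AP0302 with contralateral vehicle; vehicle with contralateral vehicle), together with a total column.

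Use the same grouping for the shift tables and carry it into the separate SAP before database lock. Grouping by product received suits a Safety Population that section 14.1 defines by dosing. The by-treatment medication tables show that the layout is feasible.

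No change is proposed to the reporting of arm-specific adverse events; the sponsor need only confirm that the text not visible here states their unit and denominator.

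The cost is one replaced sentence and extra table columns. No new data are needed, and the design and sample size do not change.

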#### 10.3.4 Clinical Laboratory Tests

The subjects are not required to be in the fasted state for the clinical laboratory testing. Laboratory testing (multiphasic chemistry panel, hematology panel, coagulation, and urinalysis) will be performed at the Screening Visit and on Day 3 at 54 hours post T0. Screening laboratory tests must be reviewed for clinical significance prior to exercise at the Exercise Visit on Day -1 or 2.

[figure not shown]
Urine drug screens and alcohol breath tests will be performed at the Screening Visit, at the Exercise Visit, and on Day 1 prior to the first dose. Urine dipsticks will be used for the urine drug screens.

In women of childbearing potential (WOCBP; women who have experienced menarche and are not postmenopausal or permanently sterilized [by tubal ligation, hysterectomy, or bilateral salpingectomy]), urine pregnancy tests will be performed at the Screening Visit, Exercise Visit and on Day 1 (pre-dose).

CBI

:

[figure not shown]
CBI

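### Section 14.5, read as written, pools laboratory change from baseline across the randomised groups; the plan should state that it is summarised by treatment group as well as overall

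*Combined protocol and SAP*

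**What the plan says.** Section 14.5 (Safety Analysis) gives one rule with one exception: "All safety-related data will be summarized as an overall group except AEs related to the area of application". Its reason begins "Since all subjects will receive vehicle on the dominant arm in addition to blinded study drug on the non-dominant arm", from which it follows that some subjects are exposed to both products.

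For laboratory data the same section says "Changes from baseline in chemistry, hematology, coagulation, and urinalysis parameters will be summarized descriptively" and names no grouping. The low/normal/high shift tables are treated differently: out-of-range shifts from "baseline (in frequency counts) will be created and presented by treatment". It adds: "All laboratory results will be listed". Medication tables are also split: "Summary tables will be generated by treatment for both prior and concomitant treatments".

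On timing, section 10.3.4 says laboratory testing "will be performed at the Screening Visit and on Day 3 at 54 hours post T 0", and "Screening laboratory tests must be reviewed for clinical significance prior to exercise at the Exercise Visit". Section 11.7 adds a draw at early termination, and the schedule in Appendix 1 agrees. In the readable text, Screening is the only draw before dosing.

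Section 7.1 makes safety the secondary objective. Section 14.2 sets 1:1 allocation and section 14.3 plans 125 subjects per group. Section 14 leaves detailed methods to an SAP signed off before database lock; no such text is in the readable pages.

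**The concern.** Laboratory change from baseline is safety data and is not the stated exception, so a programmer following the text would produce one pooled column. The only laboratory display promised by treatment would be the shift table. That shows who crossed a reference limit but not how far values moved. It misses movement within range and further movement beyond a limit already crossed.

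The reason offered for pooling does not reach blood and urine results. Vehicle on the dominant arm is given to everyone, and only subjects randomised to active receive active drug. For any systemic measure, active against vehicle on the non-dominant arm is still a clean randomised contrast.

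Pooling matters more here than in most trials because every subject exercises between the two draws. The plan itself expects exercise to bear on laboratory results: section 6.2 is headed with that subject, although its body is redacted. A pooled change mixes what exercise and elapsed time do with what the drug does. The pre-exercise baseline is not itself a fault, since it is the same in both groups. The fault is pooling over it.

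**Working it through.** **Reading the text.**

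| Display in 14.5 | Grouping stated | Grouping that results |
|---|---|---|
| General rule | Overall, except application-area AEs | Overall |
| Laboratory change from baseline | None | Overall, by the general rule |
| Laboratory shift tables | By treatment | By treatment |
| Laboratory listings | Every result listed | Not a summary |
| Medication tables | By treatment | By treatment |

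No readable sentence assigns laboratory change to treatment groups. The shift-table row departs from the general rule within the same block of text, so the section is not consistent with itself.

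**Inputs.** Allocation is 1:1 (14.2). The planned size is 125 per group (14.3), and 2 × 125 = 250 agrees with the stated total. The power basis in 14.3 is redacted and is not needed.

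**What a pooled mean contains.** Let E be the mean change common to both groups (exercise, time) and D the additional mean change due to the drug, both in units of the within-group SD of change. The vehicle mean is E and the active mean is E + D. With equal groups:

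- pooled mean = [E + (E + D)]/2 = E + D/2
- pooled SD = √(1 + D²/4), assuming equal within-group SDs

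The values of E and D below are assumptions, chosen to give the same pooled mean:

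| E | D | Pooled mean | Pooled SD | Vehicle mean | Active mean |
|---|---|---|---|---|---|
| 1.00 | 0 | 1.00 + 0 = 1.00 | √1 = 1.00 | 1.00 | 1.00 |
| 0.75 | 0.50 | 0.75 + 0.25 = 1.00 | √1.0625 = 1.03 | 0.75 | 1.25 |
| 0.50 | 1.00 | 0.50 + 0.50 = 1.00 | √1.25 = 1.12 | 0.50 | 1.50 |

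A pooled table cannot tell no drug effect from an effect of a full SD. The means are identical. The SDs differ little, and the within-group SD needed to judge them would not be shown.

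**What by-group columns would show.** The 95% CI half-width for the difference in mean change is 1.96 × √(2/n) SD:

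- n = 125 per group (planned): 1.96 × √(2/125) = 0.248, about ±0.25
- n = 112 per group (assumed number with Day 3 values): 0.262, about ±0.26
- n = 100 per group (assumed): 0.277, about ±0.28

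At 125 per group the three rows above would give intervals for D of −0.25 to 0.25, 0.25 to 0.75, and 0.75 to 1.25. The plan calls for descriptive summaries, so no such interval need be reported; it shows how much information the planned sample holds.

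**The case against.** The strongest reply is that pooling of this table is inferred. The laboratory sentence is silent, and the same block of text presents shift tables by treatment, so a by-treatment reading of all laboratory summaries is open. Those shift tables are themselves a randomised comparison with the exercise effect common to both groups, and the listings allow by-group means to be built later. Column layout is the kind of detail usually settled in an SAP, which may already add the split. The algebra holds for any pooled 1:1 table, and E and D are invented.

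Much of this stands as a limit. The sponsor may well have intended a split, and what is lost is one display, not the data. But the sentence in 14.5 is an explicit rule with a single exception, and silence under such a rule means pooled. Shift tables do not show size of change. A by-group table built later from the listings would be unplanned. If the SAP already has the split, nothing more than aligning 14.5 is needed.

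Two further points are fair. The medication tables are weaker evidence of inconsistency, because medications are not among the safety variables in the synopsis; the shift tables carry that argument. The same rule also covers AEs away from the application area, vital signs, ECGs and physical examinations, for which 14.5 states no by-treatment table. That widens the question and does not weaken the laboratory point.

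**Conclusion.** The concern holds. As written, 14.5 pools laboratory change from baseline, and the reason it gives does not justify that for systemic measures. The resulting mean, E + D/2, cannot isolate a drug effect at any sample size, whereas the planned 125 per group would place the difference within about ±0.25 SD. The identity rests on 1:1 allocation. The interval width also assumes equal within-group SDs and complete Day 3 values, and it widens only to ±0.28 SD at 100 per group. Nothing here rests on assumed enzyme levels; the analyte panel is redacted.

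This should be corrected, but it does not threaten the trial's validity. No endpoint, test or sample changes, and the underlying data are kept. Confidence is medium because the pooling comes from a general rule and the SAP has not been seen.

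**What to change.** In 14.5, or in the SAP before database lock, state that laboratory values at Screening and at Day 3 (or early termination), and the change from baseline, will be summarised descriptively by randomised treatment group and overall, next to the by-treatment shift tables. Amend the overall-group sentence so that it no longer covers laboratory data. While that sentence is open, the sponsor could decide whether the other systemic safety data should also be shown by group.

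An optional addition is by-group counts at multiples of the upper limit of normal for any muscle- and liver-related analytes in the panel.

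The cost is one sentence and extra columns in a table already planned, with no new sample, visit or staff. The drawback is a few more descriptive comparisons without multiplicity control.

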#### **14.6 Demographics and Baseline Characteristics**

Demographic characteristics will be listed by subject and will be summarized descriptively. Medical history will be coded using MedDRA and summarized by SOC and preferred term.

## **15 REGULATORY AND ETHICAL ISSUES**

### **15.1 Institutional Review Board/Independent Ethics Committee**

It is the responsibility of the investigator to have prospective approval of the study protocol, protocol amendments, informed consent documents, and other relevant documents, eg, recruitment advertisements, if applicable, from the IRB/IEC. All correspondence with the IRB/IEC should be retained in the Investigator File. Copies of IRB/IEC approvals should be forwarded to Aponia Laboratories, Inc.

Any changes to the protocol will require approval of the sponsor, in writing, and the IRB/IEC prior to implementation. The only circumstance in which an amendment may be initiated prior to IRB/IEC approval is where the change is necessary to eliminate apparent immediate hazards to the subjects. In that event, the investigator must notify the IRB/IEC and Aponia Laboratories, Inc. in writing immediately after the implementation.

### **15.2 Ethical Conduct of the Study**

The study will be conducted in accordance with the protocol, the FDA, applicable local regulatory requirements and laws, as well as the general principles set forth in the International Ethical Guidelines for Biomedical Research Involving Human Subjects (Council for International Organizations of Medical Sciences 2002), Guidelines for Good Clinical Practices (GCPs) (International Conference on Harmonisation of Technical Requirements for Registration of Pharmaceuticals for Human Use [ICH] 1996), and the Declaration of Helsinki (World Medical Association 2008). The rights, safety, and well-being of the study subjects are the most important consideration and prevail over the interests of science and society. All personnel involved in the conduct of this study must be qualified by education, training, and experience to perform their assigned responsibilities.

